5.13.4 Neurological Examinations

For the complete neurological examinations performed, the proportion of subjects reporting results of “Normal”, “Abnormal”, and “Not Done” will be calculated and presented for each scheduled time point, neurological system and treatment group. The proportion of subjects that report changes in follow-up neurological examinations (e.g. Worsened/New/Improved or Not Done/No Change) will be calculated and presented by neurological system and treatment group across visits.

A listing of all neurological examination data will be provided to supplement the tabulated results.

5.13.5 Physical Examinations

For the complete physical examinations performed, the proportion of subjects reporting results of “Normal”, “Abnormal”, and “Not Done” will be calculated and presented for each scheduled time point, body system and treatment group. The proportion of subjects that report changes in follow-up physical examinations (e.g. Worsened/New/Improved or Not Done/No Change) will be calculated and presented by body system and treatment group across visits.

A listing of all physical examination data will be provided to supplement the tabulated results.

5.13.6 Concomitant Medications

Concomitant Medications will not be tabulated but will be provided in a listing by treatment group and subject.

5.14 Long Term Follow-up

A separate Analysis Plan defining specific comparisons of interest will be developed prior to the first subject completing Stage II (one year of VNS). Data from Stages II and III, long term follow-up, will be summarized by the original treatment group assignment. For the control group, the FM-A change from Visit 7 (end of Stage 1), to Visit LT1 (1 day after VNS treatment), will be compared to the change from Visit 4 to Visit 5 with a paired-t test to evaluate the effect of VNS treatment. Maintenance of response, changes over time and after treatment modification will also be summarized with descriptive statistics. Long-term assessments will be collected for as long as the subject receives treatment. However, the key long-term assessments will be provided at 3, 6, 9, and 12 months. The analysis will assess continuation of benefit (maintenance of response and changes over time) on each assessment through the 12-month assessment. Additional exploratory analyses may be performed based on the nature of the follow-up data encountered.

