3 STUDY DESIGN

This protocol is a pivotal study of up to 120 subjects and 15 clinical sites. All subjects are implanted with the Vivistim System[®] and then randomized to either study treatment or active-control treatment. Study treatment is vagus nerve stimulation (VNS) delivered during rehabilitation. Active control treatment is rehabilitation (standard-of-care treatment) with only a minimal amount of VNS at the start of each session intended to support blinding.

This study has three distinct stages:

Stage I – blinded, with consent, assessment, implant, baseline assessment, acute therapy (6 weeks), and follow-up assessment periods (Days 1, 30 and 90 post-acute therapy)

Stage II – unblinded follow-up, including additional therapy sessions and quarterly assessments through one year post implant. Control group subjects crossover to VNS treatment.

Stage III - annual (yearly) follow-up through commercial approval to allow the device to remain implanted and the subject to continue at-home use. Additional rehabilitation sessions are allowed at the investigator's discretion.

This statistical analysis plan (SAP) is focused on Stage I (blinded, randomized portion). A future SAP will focus on Stage II and Stage III, and will be developed prior to the first subject completing Stage II (first subject reaching one-year post implant).

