3.3 Study Schedule and Treatment

Stage I: Subjects will be screened and assessed for upper limb paresis associated with stroke using a detailed stroke history evaluation (including type, location, onset, neurological evaluation, etc.) and various assessment scores to determine the level of disability in performing everyday tasks. Clinical evaluations by a stroke expert will confirm subjects entering the study exhibit a moderate to severe motor impairment in the upper extremity (UE) (as indicated by a FMA-UE score of 20 to 50) and have at least a nine-month history of the disorder. After informed consent signature, repeat assessments and other measurements will be recorded prior to randomization. Subjects will maintain their group assignments through Visit 7 (end of Stage I, assessment follow-up).

Subjects will start study therapy after an approximately one-week recovery period after surgery. This time period may vary depending on schedules and subject recovery times. The assessments after surgery, and before treatment (Visit 4) will be the baseline for statistical analyses. After a 6 week acute treatment period, post treatment assessments will be done at Visit 5 (1 Day post treatment), Visit 6 (30 Days post treatment), and Visit 7 (90 Days post treatment). During this 90 day post treatment period, subjects will not receive in-clinic rehabilitation, but are given a magnet to swipe just prior to performing their in-home rehabilitation for 30 minutes daily. The magnet activates VNS in the VNS group subjects but does not activate VNS in the Control subjects.

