Stage II: Stage II begins after Visit 7 (Day 90 post treatment). It will be the Investigator's and subject's decision to continue treatment during this unblinded follow-up stage. The intent is that all subjects will be followed through at least 12 months of post-acute study. All original VNS group subjects continue at-home rehabilitation and home-initiated stimulation for 30 minutes daily and all original Control group subjects start a 6-week rehabilitation session plus active VNS. The assessments at Visit 7 will serve as Baseline for Stage II. The control subjects will have 6 weeks of rehabilitation sessions plus active VNS treatment, followed by assessment Visits LT1 (Day 1 after the 6 week treatment), LT2 (Day 30 post treatment) and LT3 (Day 60 post treatment; at Month 3 of Stage II). All subjects will then have Visits LT4 (Month 6 of Stage II) LT5 (Month 9) and LT6 (Month 12). Different stimulation settings may be tried during the long-term therapy, especially in non-responders (those with less than a 6-point FMA-UE change).

Study guidelines allow subjects to continue at-home stimulation for 30 minutes a day while performing rehabilitation movements at home, as designated by the therapist.

All continuing subjects will have two more in-clinic rehabilitation sessions with VNS for one week (“booster sessions”), approximately one month prior to LT4 (Month 6), and LT6 (Month 12) assessments. Subjects will also be able to utilize daily subject-initiated stimulation during in-home rehabilitation.

Stage III: After Stage II of VNS therapy, subjects who wish to continue VNS use must have at least annual follow-up visits. Those who do not have annual visits or who wish to discontinue will have their device systems explanted.

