5 STATISTICAL METHODOLOGY AND ANALYSES

5.1 General Considerations

All descriptive summaries will be reported by treatment group. All summaries of continuous data will be presented as means (SD), and/or with medians with min/max as appropriate. Count data will be presented as number within each treatment group and % of subjects within each group. 95% confidence intervals will also be provided for the efficacy endpoints. All unscheduled assessments will be excluded from summary tables. Data from unscheduled assessments will be displayed in listings.

In Stage I, the control subjects will be compared against the active VNS subjects, with null hypothesis of equal change from baseline (Visit 4) in the FMA UE score between the two groups. For the control subjects in Stage II, Day 1 post treatment (LT1) will be compared against Visit 7 (end of randomization/Stage I) to determine treatment effect, with null hypothesis that there is no change from Visit 7 to LT1. All data analyses and statistical testing will be conducted using SAS Version 9.4 or higher. Unless specified for a specific test, a significance level of $\alpha = 0.05$ will be used.

Analyses outside of this SAP maybe performed to supplement results or for research purposes at the discretion of MicroTransponder, Inc.

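### The Section 5.14 paired t-test in crossed-over controls estimates the VNS effect plus any order and unblinding effects, so it should be reported as descriptive and reconciled with Section 5.1 (minor)

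*SAP*

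**What the plan says.** Section 5.14 takes two gains in the same control subjects: Visit 7 to LT1 (the second course) and Visit 4 to Visit 5 (the first). It says that the former "will be compared to the change from Visit 4 to Visit 5 with a paired-t test to evaluate the effect of VNS treatment".

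The design sections show how the two courses differ:

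- **Content and order.** In Stage I controls have rehabilitation with only a few blinding stimulations at the start of each session. In Stage II, "all original Control group subjects start a 6-week rehabilitation session plus active VNS" (Section 3.3). The order is the same for every control.
- **Blinding.** Stage I is blinded. Section 3 describes Stage II as "unblinded follow-up, including additional therapy sessions and quarterly assessments through one year post implant".
- **The interval.** Section 3.3 says "During this 90 day post treatment period, subjects will not receive in-clinic rehabilitation", and the same sentence goes on to say that they are "given a magnet to swipe just prior to performing their in-home rehabilitation for 30 minutes daily". In controls the magnet does not activate VNS.
- **Continuation.** "It will be the Investigator's and subject's decision to continue treatment during this unblinded follow-up stage" (Section 3.3). The next sentence there states the intention to follow everyone for at least 12 months.

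Section 5.1 also addresses the treatment effect in crossed-over controls. There LT1 is compared with Visit 7, "with null hypothesis that there is no change from Visit 7 to LT1". The Section 4.4 table lists the crossover comparison as LT1 against Visit 7 and rates it as other.

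**The concern.** The stated purpose is to evaluate VNS, but the null hypothesis of the paired test is that the two courses give equal mean gains. That is the same as no VNS effect only if a second course without VNS would have gained as much as the first did. The SAP neither states that assumption nor has data to check it, because no arm has a second six-week in-clinic course without VNS. The VNS group continues home exercise with stimulation in Stage II.

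The second course differs from the first in its place in the sequence, in its starting level and in blinding. If these reduce the second gain, a real VNS effect may be missed. If they increase it, VNS is credited with a gain that it did not cause. Either result would carry a p-value labelled as an evaluation of VNS.

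Section 5.1 adds a documentary problem. It puts the same question to a different null, under which any gain from the second course, including gain from rehabilitation itself, counts as treatment effect.

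**Working it through.** **1. Inputs.** From Section 3.4: 50 subjects per group, SD of change 4.0, planned gains 7.5 (VNS) and 5.2 (control), difference 2.3. From Section 5.1: default alpha 0.05. Assumed, because the SAP does not give them: a two-sided test (stated in Section 5.4 for the primary and secondary endpoints only), the same SD for both gains, the correlation ρ between a control's two gains (0 to 0.5), and the order effect. All 50 planned controls are taken to contribute pairs.

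**2. The plan's own figure.** The SAP gives no figure for the paired test, so the primary calculation is the check. Noncentrality = 2.3 / (4.0 × √(2/50)) = 2.3 / 0.80 = 2.875. On 98 df the power is 81.2%, against the stated 80%. The planning values reproduce.

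**3. What the contrast estimates.** Let R be the mean first-course gain, V the VNS effect, and O everything else by which the second course differs (order, starting level, unblinding). Then

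E[(LT1 − V7) − (V5 − V4)] = (R + O + V) − R = V + O.

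The planned data cannot separate V from O.

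**4. Standard error.** SE = 4.0 × √(2(1 − ρ)) / √50. This is 0.80 at ρ = 0 and 0.57 at ρ = 0.5.

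**5. Rejection rates.** Noncentral t with 49 df and noncentrality (V + O) / SE. For example, with V = 0 and O = 1 the noncentrality is 1/0.80 = 1.25 or 1/0.57 ≈ 1.77.

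No VNS effect (V = 0), two-sided rejection at nominal 5%:

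| Order effect (either sign) | ρ = 0 | ρ = 0.5 |
|---|---|---|
| 0 | 5% | 5% |
| 0.25 | 6% | 7% |
| 0.5 | 9% | 14% |
| 1 | 23% | 41% |
| 2 | 69% | 93% |

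True VNS effect 2.3, probability of rejecting in favour of the VNS course:

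| Order effect | ρ = 0 | ρ = 0.5 |
|---|---|---|
| 0 | 80.5% | 97.9% |
| −0.5 | 60% | 88% |
| −1 | 36% | 62% |
| −2 | 5.6% | 7.5% |
| −2.3 | 2.5% | 2.5% |

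In the last row the order effect cancels the whole planned VNS effect. For scale, 1 point is about one fifth of the planned control gain (1/5.2 = 19%).

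**6. The Section 5.1 null.** Suppose VNS does nothing and the second course yields the planned control gain of 5.2. The one-sample noncentrality is 5.2 / (4.0/√50) = 5.2 / 0.57 ≈ 9.2, and the no-change null is rejected more than 99.9% of the time. A rehabilitation gain of only 2 points would already give 93%.

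**The case against.** **Scope.** Sections 1 and 3 confine this SAP to Stage I, and Section 5.14 itself opens by leaving the comparisons of interest to a separate plan. The crossover analysis is outside the testing hierarchy in Section 5.4. This stands and limits the weight. It does not remove the point, because Section 5.14 already names the visits, the test and its purpose, and the later plan may inherit them as prespecified.

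**Size.** A reader might infer that any order effect makes the test reject or miss for the wrong reason. The figures do not support that. At 0.25 point false rejection is 6–7%, and even at 1 point the test usually does not reject. The direction is also unknown: a second course could gain less (already trained) or more (unblinded expectation).

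**Lost ground and selection.** A reader might infer that controls decline over the 90 days and then regain, or that the pairs come from a self-selected subset. The documents show neither. Controls exercise at home daily in that interval, and the intention is to follow all subjects. A paired contrast uses the same people in both periods, so selection biases it only if continuing depends on their gains. That is possible but not shown.

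**The better of the two tests.** The Section 5.14 contrast at least subtracts a gain obtained without therapeutic VNS, and the Section 5.1 test does not. This is correct, so replacing the former with the latter would make matters worse.

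**An interval is a test in disguise.** A 95% CI for the paired difference excludes zero exactly when the t-test rejects at 5%. This is also correct. What the fix changes is the stated purpose and the stated assumption.

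**Conclusion.** The point holds as a minor one. Section 5.14 gives a causal purpose to a within-control contrast that estimates the VNS effect plus order and unblinding effects. It tests for no VNS effect only if those other effects are zero. The distortion grows with their size: it is slight at a quarter of a point and serious at 1 to 2 points. These figures rest on the Section 3.4 planning values and on an assumed correlation and order effect. The document does not show how large the bias is, or its direction.

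Sections 5.1 and 5.14 also set different nulls for the same question, and that needs no assumed figure to establish.

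It would be wrong to infer that the trial's efficacy conclusion is at risk. The randomised primary comparison and the three secondary endpoints do not use this contrast.

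**What to change.** In Section 5.14, and again in the Stage II plan:

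1. Remove the stated purpose of evaluating the VNS effect. Call the analysis a descriptive within-control comparison, and report (LT1 − V7) − (V5 − V4) as an estimate with a 95% CI and no p-value.
2. State that reading this difference as a VNS effect assumes no order or unblinding effect, and that the design cannot check this.
3. Show V7 − V5 (change over the 90 days) and LT1 − V5 beside it, so that any loss and regain is visible.
4. Reconcile Section 5.1 by making the Visit 7 to LT1 change descriptive too, not a test of treatment effect.
5. State that the VNS effect is inferred only from the randomised Stage I comparison.

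The cost is SAP wording and two extra descriptive rows from assessments already scheduled. The sponsor gives up a causal significance statement from the uncontrolled crossover.

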7 TABLES, LISTINGS, AND FIGURES

The table of contents for the tables, listings, and figures (TLFs) specific to the summaries and analyses described within this SAP for the CSR will be finalized outside of this SAP. Unless changes are made to the summaries and analyses described above, the SAP will not be amended to reflect specific TLFs.

8 APPENDICES

None.
